#### **4.2.7.2.3 Time to first nasal polyp surgery and/or SCS for NP up to Week 52**

Time to first nasal polyp surgery and/or SCS for NP up to Week 52 as well as time to first nasal polyp surgery will be analysed as described in Sections 4.2.7.1.4 and 4.2.7.1.5 respectively using the actual date of surgery for NP as per Section 3.3.3.

#### **4.2.7.2.4 Time to first SCS for any reason up to Week 52**

Time to first SCS for any reason will be analysed using the Cox proportional hazards model described in Section 4.2.7.1.6. The cumulative proportion of participants receiving SCS for any reason will be estimated by Kaplan-Meier methods.

### **4.2.8 Other Secondary Endpoints**

For other secondary endpoints, nominal p-values will be presented when appropriate.

#### **4.2.8.1 Change from baseline over time in NPS and NCS through Week 52**

The same methods described in the primary analyses for the co-primary endpoints in Sections [4.2.6.1](#) (primary estimand) and [4.2.6.2](#) (US FDA primary estimand) will be used each timepoint through Week 52. Descriptive statistics including number of participants, mean, standard error, and LS means will be provided for each timepoint. In addition, the difference in LS means and the corresponding 95% CI will be provided along with the nominal p-values for each timepoint.

#### **4.2.8.2 Change from baseline in loss of smell evaluated by UPSIT test at Week 52**

The UPSIT scores will be analysed overall at Week 52. The same methods as described in Section [4.2.6.1](#) (primary estimand) will be applied.

Additionally, the number (%) of participants with anosmia will be summarised by treatment group at baseline and Week 52 separately for men and women according to [Table 7](#).

The same methods will be applied to each timepoint through Week 52.

#### **4.2.8.3 Change from baseline in modified LMK score and sinus severity score at Week 52**

The same methods as described in Section [4.2.6.1](#) (primary estimand) will be applied for modified LMK score and sinus severity score at Week 52. The same method for LMK score will be applied to each timepoint through Week 52.

#### **4.2.8.4 Change from baseline in NPSD domain scores through Week 52**

The same methods as described in Section [4.2.6.1](#) (primary estimand) will be applied to each item in the NPSD.

#### **4.2.8.5 Change from baseline in NPIF through Week 52**

The change from baseline in NPIF through Week 52 will be analysed using similar method as described in Section [4.2.6.1](#) (primary estimand). Step 1-3 will be repeated with no changes. In Step 4 post-surgery assessments will be replaced with WOCF (WPS not known). Each of the imputed datasets will be analysed using the analysis of covariance (ANCOVA) model shown in Section [4.2.6.1](#) through 52 weeks.

#### **4.2.8.6 Change from baseline in ACQ-6 at Week 52 (co-morbid asthma/AERD/NSAID-ERD subset)**

The same methods described in Section [4.2.7.1.8](#) will be applied to ACQ-6 at Week 52. The same methods described in Section [4.2.7.2.2](#) through Week 52 will be applied.

The number and proportion of ACQ-6 response status and asthma control status as defined in Section [3.4.8](#) will be summarized descriptively. The proportion of responders will be analyses as described in [4.2.7.2.1](#).

The same methods will be applied to each timepoint through Week 52.

#### **4.2.8.7 Proportion of participants with $\geq 1$ point reduction or $\geq 2$ points reduction in NPS at Week 52**

A participant with  $\geq 1$  point reduction or  $\geq 2$  points reduction in NPS at Week 52 in the absence of SCS for NP, biologic for NP, or NP surgery at or prior to that time point will be defined as a responder, otherwise the participant will be defined as a non-responder. The number and proportion of responders at Week 52 will be summarised descriptively. The proportion of responders will be analysed as described in 4.2.7.2.1.

The same methods will be applied to each timepoint through Week 52.

#### **4.2.8.8 Exposure of SCS**

Exposure of SCS over 52 Weeks will be summarised descriptively by treatment group. The number of days of SCS as well as the number of courses taken per participant will also be presented. Total SCS dose for NP (converted to prednisolone equivalents) will be summarised by treatment group. The same summary will also be provided for SCS for any reasons and for SCS for any reason excluding NP.

The number of courses of SCS for NP per year will be analysed using a negative binomial model. The response variable will be the number of courses of SCS for NP received by a participant over the planned treatment period. The model includes treatment group, baseline co-morbid asthma/AERD/NSAID-ERD status, prior NP surgery status, and region (based on eCRF) as factors. The logarithm of the time at risk (in years) will be used as an offset variable, to adjust different follow-up times. Time during a course will not be included in the calculation of time at risk.

The time at risk over 52 weeks (year) for a participant will be derived as follows:

*The time at risk over 52 weeks (years) = [planned treatment period (days) as presented in Section 3.1.3 – sum of duration of all SCS courses over planned treatment period (days)] / 365.25.*

*Duration of SCS course (days) = end date of SCS course – start date of SCS course + 1.*

#### **4.2.9 Exploratory Endpoints**

##### **4.2.9.1 Change from baseline in NPS and NCS over time up to Week 76**

To explore the off-treatment effect, change from baseline in NPS and NCS over time up to Week 76 will be analysed using the Additional FU Analysis Set. All the following steps will be performed on Additional FU Analysis Set.

**Step I:** For the data after Week 52 and up to Week 76, set data collected after date of surgery, SCS for NP, or biologic for NP treatment to missing.

**Step II:** Merge the dataset from Step I with each MI dataset from Step 3 in Section 4.2.6.1.

**Step III:** Based on the dataset from Step II, the intermittent missing data after Week 52 and up to Week 76 will be imputed using the MCMC method in SAS PROC MI with an IMPUTE=MONOTONE statement for each treatment group separately. For the NPS, the imputation model will include baseline co-morbid asthma/AERD/NSAID-ERD status, prior surgery status, region, baseline value, all post-baseline timepoints up to Week 76. For the NCS, the imputation model will include baseline co-morbid asthma/AERD/NSAID-ERD status, prior surgery status, region, baseline value, data at Weeks 12, 24, 36, 48, 50, 52, and all timepoints after Week 52 and up to Week 76. Timepoints prior to Week 52 may be further reduced from the model in case of convergence problems. NIMPUTE=1 and MAXITER=5000.

**Step IV:** The remaining monotone missing data will be imputed using the MI procedure with the 'MONOTONE REG' option for each treatment group separately. The same imputation model as in Step III will be used. NIMPUTE=1 and MAXITER=5000.

**Step V:** In the datasets from Step IV, replace post-surgery score with WPS, and replace post-SCS/biologic for NP score with WOCF. If a participant received both NP surgery and SCS for NP/biologic for NP, scores post-surgery will be set to WPS.

The same ANCOVA model described in the primary analyses for the co-primary endpoints in Section 4.2.6.1 (primary estimand) will be used for the timepoints up to Week 76. Descriptive statistics including number of participants, mean, standard error, and LS means will be provided for each timepoint. In addition, the difference in LS means and the corresponding 95% CI will be provided for each timepoint. The LS means and 95% CI over time will be displayed graphically by treatment group.

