should be checked by investigators during the study period. If a participant cannot tolerate MFNS or equivalent INCS during screening period, the participant should be screen failed.

The Principal Investigator should ask participants about SCS (oral and/or, parenteral) use for NP at each visit and record in the eCRF. Participants who require SCS and/or hospitalisation for an asthma exacerbation (see Section 8.2.5.2) or nasal polyp exacerbation during the screening period, should be screen failed and may rescreen once their symptoms improve (see Section 5.4.1).

Participants who experience an asthma exacerbation or worsening of nasal polyposis symptoms during the screening/run-in period (before Visit 2), may extend their screening period to accommodate the time needed for a short course (5-7 days) of systemic corticosteroids (SCS) treatment and return to Visit 2 no sooner than 4 weeks after the last dose of oral corticosteroids. If asthma exacerbation or worsening of nasal polyposis symptoms that require SCS or hospitalisation occurred between Visit 2 and Visit 3 (randomisation), participants should be screened failed and may be rescreened once their conditions are stabilised.

Participants will be provided with an electronic patient reported outcome (ePRO) device to record symptoms throughout the study (see Section 8.1.2). Participants who continue to meet eligibility criteria will be randomised 1:1 at Visit 3 (Day 0) to receive either placebo or tezepelumab 210 mg SC at randomisation (Week 0) and every 4 weeks thereafter (Weeks 4, 8, 12, 16, 20, 24, 28, 32, 36, 40, 44, 48). A total of 13 doses will be administered. An EOT Visit will be conducted at Week 52.

The first approximate 200 randomised participants will have a 24-week follow-up (FU) period without IP administration to assess durability of benefit. These participants will have the final safety assessment at Week 76. The remaining participants will be followed for 12 weeks after the end of treatment visit, with the final safety assessments at Week 64.

If for any reason a participant in the first set of randomised participants, as described above, is not willing to participate for a full 24-week FU period and would like to terminate participation in the study, the follow-up discontinuation (FUD) visit should be performed. The FUD visit should occur at V19 (Week 64).

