#### 1.1.5 Exploratory Objectives

Objective:	Endpoint/Variable
To explore the off-treatment effect and the recurrence rate of nasal polyps after discontinuation of treatment with tezepelumab	
 
• Change from baseline in NPS
 
• Change from baseline in bi-weekly mean NCS
 
• Participants requiring surgery and SCS for NP
 

To explore the effect of tezepelumab on exploratory biomarkers of inflammation and nasal polyposis disease and investigate biomarkers for predicting response to tezepelumab	
Exploratory biomarker parameters:
 
 
• Serum and plasma for protein biomarkers
 
• Whole blood for transcriptomic profiling
 
• Nasal epithelial lining fluid for protein biomarkers
 
• Nasal polyp biopsies for inflammatory cells by histology and immunohistochemistry, and transcriptomic profiling
 

To explore tezepelumab PK in nasal epithelial lining fluid	
 
• Exploratory PK concentrations in nasal epithelial lining fluid
 

Optional exploratory genomics sample	
 
• A blood sample for DNA isolation will be collected from participants who have
 

Objective:	Endpoint/Variable
	consented to participate in the genetic analysis component of the study.
To evaluate the effect of tezepelumab on unplanned health care resource utilization	
 
• Hospitalisations, emergency room, unplanned out participant visits, and urgent care visits.
 

To evaluate the participant reported quality of life outcomes	
 
• Short form 36-item health survey version 2 (SF-36 v2)
 
• European quality of life-5 dimensions-5 levels (EQ-5D-5L)
 
• Work productivity and activity impairment (WPAI)
 

Participant perception of overall symptom severity and change	
 
• Patient Global Impression of Severity (PGI-S)
 
• Patient Global Impression of Change (PGI-C)
 

To evaluate airway inflammation in participants with co-morbid asthma/AERD/NSAID-ERD	
 
• Change from baseline in fractional exhaled nitric oxide (FeNO).
 

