Two hundred participants per arm also provides at least 95% power to detect a statistically significant difference at a 2-sided 1% level in secondary endpoints of change from baseline in loss of smell, LMK, and SNOT-22 (assuming mean [SD] of -1 [1.3], -5 [5.45], and -17.4 [26.8], respectively). The size of the study also provides at least 95% power to detect a statistically significant difference at the 2-sided 1% level in the key secondary endpoint time to SCS and/or surgery for NP, assuming a true reduction in risk of 67% (hazard ratio [HR] of 0.33) with a placebo rate at Week 52 of 35% (placebo data estimated from dupilumab SINUS-52). In addition, this provides at least 80% power to detect a difference (at a nominal 5% significance level) in the key secondary endpoint of time to surgery, assuming a true HR of 0.33 and a placebo rate at Week 52 of 11% (placebo data estimated from pooled dupilumab studies SINUS-24 and SINUS-52). Assuming 50-70% of participants will have co-morbid asthma, the sample size will also provide >80% power for the co-primary endpoints at a 2-sided 5% significance level in the co-morbid asthma subgroups.

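### The Week 64 and Week 76 comparisons in SAP 4.2.9.1 carry on-treatment rescue scores forward unchanged, so they mix on-treatment rescue with any off-treatment effect

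*SAP*

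**What the plan says.** SAP 1.1.5 states the exploratory aim: "To explore the off-treatment effect and the recurrence rate of nasal polyps after discontinuation of treatment with tezepelumab". Protocol 4.1 gives about the first 200 randomised participants a "24-week follow-up (FU) period without IP administration to assess durability of benefit". SAP 4.2.9.1 supplies the model: "To explore the off-treatment effect, change from baseline in NPS and NCS over time up to Week 76 will be analysed", on the Additional FU Analysis Set. SAP 2.1.3 restricts that set to those who complete the Week 64 visit.

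The steps that matter here are these:

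- Step I, for data after Week 52: "set data collected after date of surgery, SCS for NP, or biologic for NP treatment to missing".
- Step II merges the result with the datasets from Step 3 of SAP 4.2.6.1. In those datasets the rescue scores have not yet been substituted.
- Step V is therefore the only substitution step: "In the datasets from Step IV, replace post-surgery score with WPS, and replace post-SCS/biologic for NP score with WOCF". It is not limited to rescue that began after Week 52.

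The worst possible score (WPS) is 8 for NPS and 3 for NCS (SAP 4.1.3.1). WOCF is the worst post-baseline value before systemic corticosteroids (SCS) or a biologic for nasal polyps (SAP 4.2.6.1). The outcome remains change from study baseline, and "the difference in LS means and the corresponding 95% CI will be provided for each timepoint". No p-value is listed, and only the primary estimand is named. SAP 3.5.1 likewise derives only changes from baseline for the post-treatment period.

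**The concern.** The composite strategy is a deliberate choice for Week 52, where rescue on treatment counts as a poor outcome. SAP 4.2.9.1 reuses it unchanged for a different question: what happens once the drug has gone. A participant given SCS at Week 10 has the same assigned score at Weeks 52, 64 and 76. Such participants normally stay on study drug (Protocol 8.1.4) and can reach follow-up. There the diary continues (Protocol 8.1.2.1) and NPS has Week 64 and Week 76 windows (SAP 3.1.4, Table 2). Their off-treatment scores are set aside and an on-treatment value is put in their place.

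Because the plan expects more rescue on placebo, the late between-arm difference contains a component that cannot fade. At stake is the reading of the 24-week follow-up, whose stated purpose is durability.

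**Working it through.** **Inputs from the documents.** SAP 1.3 sizes the composite rescue endpoint "assuming a true reduction in risk of 67% (hazard ratio [HR] of 0.33) with a placebo rate at Week 52 of 35" per cent. It takes 11% for surgery on placebo with the same hazard ratio, and SDs of change of 2.25 (NPS) and 1.22 (NCS). About 200 participants at 1:1 allocation gives about 100 per arm. Protocol 5.1 sets total NPS at entry at 5 or more, out of 8.

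**Assumptions, not in the documents.** Mean baseline is 6 (NPS) and 2.6 (NCS). Mean WOCF change w is 0 to +1 (NPS) or 0 to +0.2 (NCS). Mean Week 76 change m is 0 to -1 (NPS) or 0 to -0.6 (NCS). Giving m the same value in both arms represents no remaining drug effect.

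**The plan's own power first.** Tezepelumab rate = 1 - (1 - placebo rate)^HR.
- Composite: 1 - 0.65^0.33 = 13.3%. Events = 200 × (0.350 + 0.1325) = 96.5. Schoenfeld power at 2-sided 1% is 99.8% (stated: at least 95%).
- Surgery: 1 - 0.89^0.33 = 3.8%. Events = 200 × (0.110 + 0.0377) = 29.5. Schoenfeld power at 5% is 85.4% (stated: at least 80%). The Freedman and two-proportion formulas give 78.2% and 79.1%.

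**Excess of fixed scores on placebo.** Surgery: 0.110 - 0.0377 = 0.0723. SCS: (0.35 - 0.11) - (0.1325 - 0.0377) = 0.1452. Together this is about 22 percentage points.

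**Offset with no drug effect left.** Offset = -[0.0723 × (WPS - baseline - m) + 0.1452 × (w - m)].
- NPS, smallest (m = 0, w = 0): -(0.0723 × 2) = -0.14.
- NPS, largest (m = -1, w = 1): -(0.0723 × 3 + 0.1452 × 2) = -0.51.
- NCS, smallest (m = 0, w = 0): -(0.0723 × 0.4) = -0.03.
- NCS, largest (m = -0.6, w = 0.2): -(0.0723 × 1.0 + 0.1452 × 0.8) = -0.19.

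**How often the 95% CI excludes zero.** SE = SD × √(2/100), which is 0.318 for NPS and 0.173 for NCS at the planned SDs. The probability is Φ(|offset|/SE - 1.96) + Φ(-|offset|/SE - 1.96). For NCS this gives 5% to 19% at SD 1.22, and 6% to 60% at SD 0.6 to 0.8. For NPS, ANCOVA simulations on the bounded score gave:

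| Setting, no drug effect at Week 76 | NPS offset | CI excludes zero |
|---|---|---|
| 100 per arm, SD 2.25, surgery participants included | -0.27 to -0.45 | 20-36% |
| 100 per arm, SD 1.5, surgery participants included | -0.23 to -0.43 | 22-49% |
| Both of the above, plus 10% rescue after Week 52 in each arm | -0.22 to -0.42 | 18-44% |
| 90 per arm, latent SD 1.3-2.0, within-patient correlation 0.5-0.8, surgery participants included | -0.14 to -0.34 | 9-36% |
| The same, surgery participants absent | -0.06 to -0.19 | 5-14% |
| Scores not replaced, 100 per arm | 0.00 | 4.4-5.4% |

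**Change from Week 52 on the same datasets.** Where a 1.8-point effect was fully lost by Week 76, this contrast was +1.4 to +1.6 NPS points, and its CI excluded zero in essentially every run. Where the effect persisted in full, it averaged -0.01 and excluded zero in 5% of runs. It has two limits:
- Dilution: participants with fixed scores contribute zero change, so 0.867 × 1.8 = 1.56 is recovered of the 1.8 lost.
- Drift: if latent scores in both arms rise by d, the contrast moves by (0.867 - 0.65) × d = 0.22d with no change in drug effect. A simulation with d = 1 gave +0.27, and the CI excluded zero in 31% of trials.

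**The case against.** The strongest reply is that the planned output already shows the decline. SAP 4.2.9.1 reports and plots LS means by arm at every timepoint on one analysis set. A reader might infer that complete loss of benefit would pass as a persisting effect. The documents do not support that. In the runs with full loss, a Week 76 difference of -0.14 to -0.33 goes with a change since Week 52 of +1.4 to +1.6, so the same table would show a Week 52 difference of about -1.5 to -1.9 collapsing. ANCOVA is also linear in the outcome, so the contrast proposed below equals the reported Week 76 difference minus the reported Week 52 difference. Only its interval is new.

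A reader might also infer that recurrence is never estimated. That goes too far. Protocol Section 3 and SAP 1.1.5 list participants needing surgery and SCS under this objective. The SAP amendment history says the proportion up to Week 76 moved to an exploratory SAP, which is not available here.

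The analysis is exploratory, lies outside the testing hierarchy and lists no p-value, so 5% is a yardstick for the interval and not an error rate that the plan promises to control. Change from baseline is the variable that the protocol names. Protocol 7.1.1 requires no endoscopy after surgery that ends study drug, so a fully treatment-policy NPS analysis would lack data.

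All of this stands. It limits the consequence but does not change what the late difference contains.

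**Conclusion.** The point holds in limited form. The Week 64 and Week 76 differences in change from baseline combine on-treatment rescue with any off-treatment effect. With no drug effect left, the NPS difference is biased by roughly -0.1 to -0.5 points towards tezepelumab. Its CI excludes zero in about 5-14% of trials without surgery participants and about 9-49% with them. For NCS at SD 1.22 the rate is about 5-19%. This SAP gives no interval estimate of change in NPS or NCS after stopping.

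A false exclusion should not be taken as the usual result. At SD 2.25 the CI half-width is about 1.96 × 0.318 = 0.62, larger than any offset found.

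The size rests on full-trial planning rates, whereas the set holds Week 64 completers only. Protocol 9.2 labels the 11% a surgery-decision rate, while WPS follows actual surgery, so the WPS share may be lower. Follow-up options after stopping study drug run to Week 52 (Protocol 7.1.1), so it is uncertain whether surgery participants are in the set. The baseline means, WOCF changes and common Week 76 change are assumed.

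**What to change.** In SAP 4.2.9.1:

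1. Add change from Week 52 to Weeks 64 and 76 as the estimate of loss of effect and recurrence: LS mean by arm, between-arm difference and 95% CI, from the same Step V datasets with the same model.
2. State its limits. Participants rescued before Week 52 contribute zero change, or a step from WOCF to WPS if surgery follows later. The contrast is therefore diluted and can shift if both arms drift. It should not be described as free of the fixed scores, and it measures loss since Week 52, not the effect remaining at Week 76.
3. Keep the change-from-baseline curve, and state that its Week 64 and Week 76 difference includes on-treatment rescue and is not by itself evidence of residual drug effect.

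The cost is one further ANCOVA per timepoint on datasets already generated, plus a few sentences. No new data are needed, and the Week 52 estimands and the alpha allocation are untouched. SAP 2.1.4 rules out updates after the primary database lock, so the wording belongs in the SAP before then.

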#### 4.2.9.2 PGI-S and PGI-C

PGI-C response categories are described in Section 3.5.3. The number and percentage of participants in each category in PGI-S and PGI-C, as well as PGI-C improvement responses, will be summarised descriptively by treatment group and visit.

#### 4.2.9.3 EQ-5D-5L

The total score and change from baseline in EQ-5D-5L overall utility score of all dimensions as well as individual dimension scores will be summarised descriptively by treatment group and visit. VAS and Health State Index will also be summarised descriptively by treatment group and visit.

#### **4.2.9.4 Change from baseline in SNOT-22, loss of smell, UPSIT, NPSD TSS, and NPIF overtime up to Week 52**

The change from baseline in SNOT-22, loss of smell, and NPSD TSS will be analysed as described in Section 4.2.9.1.

The change from baseline in UPSIT will be analysed as described in Section 4.2.8.2.

Descriptive statistics including number of participants, mean, standard error, and LS means will be provided for each timepoint. In addition, the difference in LS means and the corresponding 95% CI will be provided for each timepoint. The LS means and 95% CI over time will be displayed graphically.

The change from baseline in NPIF will be analysed as described in Section 4.2.8.5.

Descriptive statistics including number of participants, mean, standard error, and LS means will be provided for each timepoint. In addition, the difference in LS means and the corresponding 95% CI will be provided for each timepoint.

